5.3.2. Pregnancy

5.3.3. Unable to provide informed consent

5.4. Study Timeline

[figure not shown]

Figure 1: Study Timeline and Procedures. Abbreviations: CF, cystic fibrosis; LC-MS/MS, liquid chromatography tandem mass spectrometry, Scr, serum creatinine

5.5. Informed Consent

5.5.1. Procedures: A member of the study team will review the study and informed consent with the potential participant and answer any questions. Written informed consent will be obtained from the patient prior to enrollment in the study. Informed consent documents will outline the risk associated with obtaining the blood samples as well as the anticipated benefits of the study. A copy of the signed informed consent will be given to the participant. Subjects will be free to opt out of the study at any time for any reason after enrollment.

5.5.2. Storage: Informed consent documents will be stored in a locked cabinet in a locked office. Copies of the informed consent documents will be uploaded onto M+Box with access restricted to IRB-authorized study personnel, and will also be uploaded to participant's medical record in MiChart.

5.6. Dosing and Administration

5.6.1. The dose and duration of infusion for PMB will be determined at the discretion of the prescribing physician in the course of routine clinical care. There is no study intervention on the dosing and administration of PMB.

5.6.2. The recommended dosing schedule for intravenous polymyxin B at Michigan Medicine consists of an initial weight-based loading dose (2 mg/kg, maximum of 200 mg) followed by 100 mg every 12 hours for the duration of therapy as determined by the clinician. A reduction of the maintenance dose to 75 mg every 12 hours is recommended for patients with total body weight less than or equal to 50 kg.

5.7. Sampling:

5.7.1. Blood samples will be collected from enrolled patients at 5 time points during a single dosing interval under steady-state conditions. Sampling will occur on any day of therapy immediately prior to and following a single dose of PMB. The infusion time is selected at the discretion of the prescribing physician; thus the sampling schema is described based on the duration of infusion (Table 1).

Table 1: Sample collection times

Sample Code	Collection Timepoint	Collection Time Relative to Duration of Infusion (t_{inf})
C_0	Prior to Start of Infusion	0 hour
C_1	End of Infusion	$t_{inf} + 0$ hour
C_2	One Hour after End of Infusion	$t_{inf} + 1$ hour
C_3	Three Hours after End of Infusion	$t_{inf} + 3$ hours
C_4	Eight Hours	8 hours

5.7.2. Blood samples will be collected via one of three sampling methodologies: peripheral venipuncture, peripheral intravenous catheter, or a central venous catheter (e.g., PICC, Port). The method of obtaining blood samples will be determined by study personnel and will consider patient preference, patient safety, and the likelihood of obtaining adequate samples. Insertion of, care for, and sampling from indwelling catheters will be performed per hospital policy.

5.7.3. The procedure for obtaining and processing blood samples can be found in the Laboratory Protocol document in the Appendix (10.1).

5.8. Demographic and Clinical data: Study team members will obtain demographic and clinic data needed to describe the study population and build pharmacokinetic models. Data will be abstracted from DataDirect or obtained directly from the medical record for each index encounter. Data recorded directly from the medical record will be stored in REDcap.

5.8.1. Demographic: comprehensive demographic data will be obtained from DataDirect. Examples of variables of interest include race and sex.

5.8.2. Encounter: comprehensive encounter data will be obtained from DataDirect. Example variables of interest include age, weight, height, body mass index, admission and discharge dates, and sites of care.

5.8.3. Diagnosis: comprehensive codified diagnosis data will be obtained from DataDirect.

Example diagnoses of interest include comorbid conditions, admission diagnoses, and discharge diagnoses

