We propose to measure the plasma concentrations of PMB in adult patients with CF receiving intravenous therapy as a part of their routine care and to use these measured concentrations to build population pharmacokinetic models. The population pharmacokinetic modeling approach will allow the assessment of the impact of patient specific covariates (i.e. weight, renal function) on pharmacokinetic parameters. Patients will be monitored for nephrotoxicity and neurotoxicity to ensure that PMB has an acceptable

margin of safety in this patient population. This investigation will be the first to prospectively assess the pharmacokinetics and toxicities of PMB in this patient population and will facilitate optimal use of this compound in the management of acute pulmonary exacerbations of CF.

4. Specific Aim/Hypothesis

4.1. Measure the plasma concentration of PMB in adult CF patients receiving intravenous therapy. Adult patients with CF often receive multiple courses of antipseudomonal antibiotics over the course of their disease resulting in the evolution of multi-drug resistant (MDR) *P. aeruginosa* pulmonary colonizers. The polymyxins, colistin and PMB, frequently retain activity against MDR gram-negative bacteria. Colistin has historically been the most commonly used polymyxin in patients with CF; however, new pharmacokinetic (PK) and toxicity data obtained from non-CF populations suggest that PMB may achieve more consistent exposure with lower associated toxicity. We aim to measure concentrations of PMB in plasma samples obtained from adult CF patients treated with polymyxin B using liquid chromatography–tandem mass spectrometry (LC-MS/MS).

4.2. Characterize the pharmacokinetics of PMB in adult CF patients. There are three major population PK studies which inform the dosing of PMB and one small study including patients with CF. These studies suggest that the clearance of PMB is not related to patient body weight and have discordant results regarding patient renal function. Therefore, underweight patient populations with excellent renal function, such as CF, may be at risk for underdosing with traditional weight-based regimens. We aim to use population pharmacokinetic modeling to characterize the PK of fixed-dose PMB in this special population and assess the effect of patient-specific covariates (e.g., body weight, renal function) on PK parameters.

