5.2.1. Adults, greater than 18 years of age

5.2.2. Diagnosed with cystic fibrosis

5.2.3. Treated with intravenous polymyxin B for a suspected or confirmed infection as part of routine care

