6.1. Population Pharmacokinetic Analysis

6.1.1. Pharmacokinetic Modeling: The PK data will be analyzed using a population PK modeling approach through the nonparametric adaptive grid (NPAG) algorithm in the Pmetrics™ package for the R environment.^{21,22} Models will be parameterized as one- and two-compartment systems with zero-order infusion and elimination from the central compartment modeled as a first-order process. Michaelis-Menten and mixed-order linear/Michaelis-Menten elimination will be tested if first-order processes alone do not display adequate fit of the data.

For all models, the inverse of the estimated assay variance will be used as the first estimate for weighting. Weighting will be accomplished by making the assumption that total observation variance is proportional to assay variance. Assay variance will be determined on a between-day basis. The analysis will be performed with adaptive γ , a scalar which is optimized with each cycle to produce the best approximation to the homoscedastic assumption.

Models will be run for at least 100 cycles and Bayesian estimates will be obtained for each patient. For each model, both the mean and median will be employed as measures of central tendency for the population parameter estimates and will be evaluated in the Bayesian analysis. Scatter plots will be examined for individual patients and for the population as a whole.

6.1.2. Monte Carlo Simulation: The parameter vector and covariance matrix from population PK modeling will be used as the prior distribution for the simulation function within Pmetrics™. 1000-subject Monte Carlo simulations will be performed for candidate dosing regimens.

The simulated plasma concentration-time curves will be used to calculate area under the concentration-time curve (AUC) values for different 24-hour increments through 96 hours. For each regimen examined, probability of efficacy will be the fraction of the simulated subjects at each time interval for which the 24-hour AUC is between 50 – 100 mg*h/L while the probability of toxicity will be the fraction of subjects with 24-hour AUC values ≥ 100 mg*h/L.^{23,24}

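### Does allowing sampling on any treatment day, when Section 5.7.1 also calls for steady state, undermine the clearance estimates?

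*Combined protocol and SAP*

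**What the plan says.** Section 5.7.1 places the five samples at "5 time points during a single dosing interval under steady-state conditions". The next sentence reads "Sampling will occur on any day of therapy immediately prior to and following a single dose of PMB". Neither Table 1, Section 6.1 nor the laboratory appendix (10.1) gives a minimum number of preceding doses or defines steady state. Figure 1, the study timeline, is not available to us and may do so.

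The local recommendation in Section 5.6.2 is an "initial weight-based loading dose (2 mg/kg, maximum of 200 mg) followed by 100 mg every 12 hours", with a lower maintenance dose at 50 kg or below; Section 5.6.1 leaves actual dosing to the prescriber. Section 6.1.1 specifies one- and two-compartment models with zero-order infusion, and "Bayesian estimates will be obtained for each patient". Aim 4.2 is to "assess the effect of patient-specific covariates (e.g., body weight, renal function) on PK parameters". Section 6.1.2 simulates AUC "values for different 24-hour increments through 96 hours". Administration records are collected under Section 5.8.5, and the appendix has staff log the actual time of each draw. The appendix plans supplies for at most 20 subjects.

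**The concern.** Read separately, the two sentences conflict: one sets a condition and the other seems to lift it. A coordinator could sample at dose 2 or 3 in good faith. If the half-life is long relative to the 12-hour interval, concentrations are then still accumulating and carry less information on clearance. That patient's Bayesian estimate would be pulled further toward the population value. With so few subjects, a handful of weakly informed clearances could blunt the weight and renal-function analysis in aim 4.2. Section 3 itself faults the only earlier study in cystic fibrosis because its renal-function relationship rested mostly on one patient. There is a second worry: if steady state were assumed in the analysis when it had not been reached, clearance would be overstated.

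**Working it through.** The plan gives no half-life, time to steady state or precision target, so there is no figure to reproduce. The check asks how much precision early sampling costs.

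**Inputs from the documents.** Sampling at 0, t_inf, t_inf + 1, t_inf + 3 and 8 h (Table 1); the Section 5.6.2 schedule every 12 h; 20 patients (10.1).

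**Assumptions.** One compartment, 1 h infusion, 15% proportional error, half-life 6 to 18 h, 30% between-subject SD on clearance (CL) and volume (V), weight 55 kg. Steady state is taken as dose 20.

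**Step 1: one patient.** Each dose D given at time t_d contributes, with s = t − t_d > 0 and k = CL/V = ln 2 / half-life,

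C = (D / t_inf) / CL × (1 − exp(−k·min(s, t_inf))) × exp(−k·max(s − t_inf, 0)),

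and contributions are summed over doses. With J the derivatives of log C with respect to (log CL, log V), F = JᵀJ / 0.15², and SE(log CL) is the square root of the CL element of F⁻¹.

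| SE of individual log CL | 6 h | 9 h | 12 h | 15 h | 18 h |
|---|---|---|---|---|---|
| Dose 2 | 0.075 | 0.133 | 0.220 | 0.319 | 0.424 |
| Dose 3 | 0.068 | 0.087 | 0.139 | 0.215 | 0.302 |
| Dose 5 | 0.067 | 0.069 | 0.081 | 0.112 | 0.163 |
| Steady state | 0.067 | 0.067 | 0.067 | 0.068 | 0.068 |

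Over 45 to 80 kg the dose-2 values run 0.071–0.076 at 6 h, 0.124–0.321 at 9–15 h and 0.422–0.431 at 18 h. Shrinkage of individual clearance at dose 2 is 6/15/30/46/59% across the five half-lives, against about 5% at steady state. A separate calculation with an added 0.1 mg/L error term gave the same pattern: about 7% relative SE at steady state, and 12% and 25% at dose 2 for half-lives of 8.3 and 12.5 h.

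**Step 2: the population.** Each patient contributes information (F⁻¹ + Ω)⁻¹, with Ω = 0.3²·I, summed over 20 patients. All at steady state: √((0.3² + 0.067²)/20) = √(0.0945/20) = 0.069. Rise in the SE of typical log CL:

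| Share sampled early | 6 h | 9 h | 12 h | 15 h | 18 h |
|---|---|---|---|---|---|
| 10% at dose 2 | 0.0% | 0.5% | 1.3% | 2.3% | 3.1% |
| 20% at dose 2 | 0.1% | 1.0% | 2.8% | 4.8% | 6.6% |
| 20% at dose 3 | 0.0% | 0.2% | 1.1% | 2.5% | 4.1% |
| 50% at dose 2 | 0.3% | 2.9% | 8.2% | 14.6% | 20.6% |

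Hand check, 20% at dose 2, 12 h, ignoring the CL–V correlation: 16/0.0945 + 4/(0.09 + 0.220²) = 169.3 + 28.9 = 198.2; 1/√198.2 = 0.071, about 3% above 0.069, in line with the table. For a covariate slope on clearance, half the patients at dose 2 raises the SE by 2.8–2.9%, 7.4–8.2% and 12.9–14.6% at 9, 12 and 15 h.

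**Step 3: what early samples buy.** Individual SE of log AUC by the delta method, half-lives 9–15 h:

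| | Dose 2 | Dose 5 | Steady state |
|---|---|---|---|
| Day 1 (0–24 h) | 0.068–0.074 | 0.110–0.188 | 0.112–0.226 |
| Day 4 (72–96 h) | 0.124–0.295 | 0.068–0.094 | 0.067–0.069 |

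Section 6.1.2 uses both windows.

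**Step 4: bias.** If the analysis assumed steady state, a dose-2 interval AUC as low as 74% of its steady-state value would overstate clearance by 1/0.74 − 1 = 35%. Section 6.1.1 makes no such assumption: the model is driven by the doses given, which Section 5.8.5 supplies.

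**The case for a change.** The strongest case for a change is that the contradiction concerns when the primary data are collected, that one phrase would cure it, and that even the charitable reading leaves staff without a definition of steady state. With half the patients at dose 2 and a half-life of 12 h or more, typical clearance loses 8–21% in precision. With a between-subject SD of 20% instead of 30%, the same scenario costs 5.2/13.4/21.5% at 9/12/15 h. Two-compartment runs also put a dose-2 patient at 13–20% relative SE even with prior information.

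The looseness of the wording stands, and so do the individual-level losses. The rest is weaker. Half the cohort at dose 2 is improbable: patients enter because they are "Treated with intravenous polymyxin B for a suspected or confirmed infection as part of routine care", and "Written informed consent will be obtained from the patient prior to enrollment in the study", so several doses will often have passed. Anyone sampled that early with a long half-life would also be outside the plan's own steady-state condition. Each possible remedy has a problem. A minimum dose number may lose patients with short courses from a study of at most 20 and weakens volume and day-1 AUC. Dropping the steady-state phrase, or listing the dose number sampled, records a detail that analysts can already derive from the administration data and alters no estimate.

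**Conclusion.** The two sentences are loosely worded, but no change is needed. Taken together they most naturally mean any day once steady state has been reached, and departures from that are handled by modelling the full dosing history. No bias follows. The cost is precision in the individual clearance of early-sampled patients: negligible near a 6 h half-life, and material at dose 2 from about 9 h upward. For typical clearance it is a rise of 0.0–6.6% in the standard error with 10–20% of patients at dose 2. It would be larger only if many patients were sampled that early and the half-life were long. Against it stands better information on day-1 exposure, so the choice of sampling day is a fair trade-off.

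This rests on assumed half-lives, residual error and between-subject variability, none of which the documents give. It also assumes that the analysts fit the recorded doses and times, which the specified model calls for. The shrinkage and population figures come from a parametric approximation and are a guide to size under NPAG, not a prediction. Figure 1 may already give the sampling day.

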5.8.4. Procedures: comprehensive procedure data will be obtained from Data Direct. Example

variables of interest include procedure codes related to renal replacement therapy or source control procedures

5.8.5. Medications: comprehensive medication orders and administration data will be obtained

from DataDirect. Example medications of interest include polymyxin B, aminoglycosides, beta-lactams, other anti-infectives, vasopressors, albumin, fluid, immunosuppressants, corticosteroids, intravenous contrast dye, and chemotherapies

5.8.6. Laboratory: comprehensive laboratory information, including microbiology, will be

obtained from DataDirect. Example laboratory values of interest include aminoglycoside or vancomycin drug concentrations, serum creatinine, blood urea nitrogen, sodium, potassium, CO₂, albumin, total bilirubin, white blood cell count, platelet count, hemoglobin, hematocrit, total lymphocyte count, pH, PaO₂, bicarbonate, procalcitonin, erythrocyte sedimentation rate, c-reactive protein, and culture results.

5.8.7. Vitals: comprehensive vital signs and fluid inputs and outputs will be obtained from

DataDirect. Example vitals of interest include mechanical ventilation, fraction of inspired oxygen (FiO₂), oxygen saturation, temperature, blood pressure, heart rate, respiratory rate, urine output, Glasgow Coma Scale score (GCS), dietary information.

5.8.8. Outcome: hospital length of stay, mortality, readmission rate. Results of spirometry, including forced expiratory volume in 1 second (FEV1).

5.9. Assay: Plasma concentrations of polymyxin B, comprising both polymyxin B1 and B2 components, will be determined using LC-MS/MS.

5.10. Storage of data and samples

5.10.1. Sample storage: Samples will be labeled with a unique study identifier and stored at -80

C. No protected health information will be stored with the samples. Access to samples will be restricted to authorized research personnel.

5.10.2. Data storage: Sample information including subject name, medical record number, and date and time of collection will be recorded separately in the sample collection log. The sample collection log will be stored in a locked draw within a locked office, accessible only to study personnel. Electronic data will be maintained in a password-protected file within M+box. Access to this document will be restricted to approved members of the research team. Only codified data will be used in analysis.

5.11. Patient reimbursement: Patients will be reimbursed \$100 for participation in the study.

6. Data Analysis

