 - i. Collect venous blood in pre-labeled and chilled lavender top plasma collection tubes
 - ii. Invert the plasma collection tube ten times slowly and gently to ensure adequate mixing of the EDTA with the sample
 - iii. Immediately replace the sample tube upright in the test-tube rack within the study cooler
 - iv. Record actual time of sample collection in sample collection log
- b. Processing
 - i. Centrifuge the whole blood at 3000 rpm for 12 minutes in a refrigerated centrifuge set to 4°C
 - ii. Transfer the supernatant (plasma) to pre-labeled cryovials in 0.5 – 1 mL aliquots of equal volume, taking care not to disturb the buffy coat.
 - 1) See the section below for management of insufficient sample volume
 - iii. Place cryovials into the appropriate cryovial boxes ordered by subject and sample code

- 1) More than one subject can be stored in each cryovial box. Do not divide a samples for a single subject between more than one cryovial box**
 - iv. Store cryovial boxes at -80°C until analysis**
 - 1) The time from blood collection until the plasma sample is stored at -80°C should be 90 minutes or less.**

c. Potential Problems

- i. Hemolysis**
 - 1) Samples with visible hemolysis may be processed as noted**
 - 2) The cryovials for hemolyzed samples should be marked with the term "Hemo"**
- ii. Insufficient sample volume**
 - 1) An insufficient sample volume is less than 0.5 mL of plasma**
 - 2) If between 0.25-0.5 mL:**
 - a) Transfer plasma to two labeled cryovials in aliquots of equal volume**
 - 3) If less than 0.25 mL:**
 - a) Transfer plasma into the cryovial labeled "AQ-1" only**
 - b) Mark the cryovial labeled "AQ-2" with the term "ISV", which indicates "insufficient sample volume"**
 - c) Place the "AQ-2" cryovial labeled "ISV" in the appropriate slot in the "AQ-2" cryovial box inverted, so that the cap is facing downward rather than upward.**

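### The log captures actual draw times but is not required to capture the sampled infusion's actual start and stop; any charting error falls mainly on Vc, less on CL and AUC24, with no fixed direction.

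*Combined protocol and SAP*

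**What the plan says.** **Infusion and sampling.** Section 5.7.1 states: "The infusion time is selected at the discretion of the prescribing physician; thus the sampling schema is described based on the duration of infusion". In that section's sampling table, C0 comes before the infusion, C1 at its end, C2 and C3 one and three hours after its end, and C4 at 8 hours. Sampling covers one dosing interval, and "Sampling will occur on any day of therapy immediately prior to and following a single dose of PMB". Earlier doses therefore also enter the dose history. Appendix I, section 2, repeats the table but describes t_inf as the end of infusion in its text and as the duration in the column heading.

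**Draw times.** Appendix I, 4.a.iv: "Record actual time of sample collection in sample collection log". Section 5.10.2 describes the log: "Sample information including subject name, medical record number, and date and time of collection will be recorded separately in the sample collection log".

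**Dose times.** Section 5.8: "Data will be abstracted from DataDirect or obtained directly from the medical record for each index encounter". Section 5.8.5, on medications: "comprehensive medication orders and administration data will be obtained", with DataDirect as the source and polymyxin B among the examples. No section asks staff to note when the sampled infusion began, ended or paused, or says how a charted dose time is reconciled with a logged draw time.

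**Model.** Section 6.1.1 specifies one- and two-compartment models with zero-order infusion. Observation variance is taken as proportional to assay variance, scaled by an adaptive gamma. There is no term for error in dose timing.

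**The concern.** The two clocks the model depends on come from different sources. Draw times are observed and written down at the time; dose times are abstracted afterwards. If the charted start or stop of the sampled dose is wrong, correctly timed draws are set against a wrong input. Gamma can absorb some of the extra scatter but cannot correct the input.

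C1 to C3 carry most of the information on central volume and distribution, so they are the samples most exposed. The estimates then feed the 1000-subject simulations in 6.1.2, which are judged at AUC24 limits of 50 and 100 mg*h/L. The supply list in Appendix I plans for at most 20 subjects with five samples each, so there is little data to dilute such errors. Infusion times that nobody recorded cannot be reliably recovered later.

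**Working it through.** The documents state no timing-error figure, so there is none to reproduce. The check is whether the mechanism holds and how large it could be.

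**Inputs from the documents.** Table 1 sampling times; 100 mg every 12 h (5.6.2, used only as a simulation input); AUC24 limits 50 and 100 (6.1.2).

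**Assumed, because the documents give no values.** CL 2 to 4 L/h; one-compartment V 20 to 40 L; two-compartment Vc 10 to 20 L, Q 2 to 6 L/h, peripheral volume 15 to 25 L; infusion 1 to 2 h; charting error 5 to 30 min; residual error 10%; between-subject SD 35 to 60%. Fits were least squares or MAP, which approximate NPAG but do not run it.

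**Formula (one compartment).** With k = CL/V and doses j running from s_j to e_j at rate R_j = 100/(e_j − s_j),

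C(t) = Σ (R_j/CL)·[exp(−k·(t−e_j)⁺) − exp(−k·(t−s_j)⁺)].

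Both s_j and e_j are inputs, so an error in either changes every prediction for that dose.

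**Worked case: CL 3, V 20, 1 h infusion, k = 0.15; the sampled dose truly starts 30 min after its charted start.**
- Steady-state peak: (100/3)(1 − e^−0.15)/(1 − e^−1.8) = 4.643/0.8347 = 5.56 mg/L. Trough: 5.56·e^−1.65 = 1.07.
- True C1, 1.5 h after the charted start: 1.07·e^−0.075 = 0.99 at the true start, then 0.99·e^−0.15 + 4.643 = 5.50. The charted input predicts 5.56·e^−0.075 = 5.16. C1 looks 6.5% too high, which pulls V down.
- If C0 was drawn before the charted start, the fit gives CL −4.6% and V −11.0%.
- If C0 was drawn just before the true start, it reads 0.99, but the charted input predicts 0.99 + (100/3)(1 − e^−0.075) = 3.40. That mismatch pushes the estimates the other way.

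**Two-compartment results, individual fits, 1 h charted infusion**

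| Scenario | CL | Vc |
|---|---|---|
| True start 15 min after charted, C0 before charted start | −2 to −5% | −5 to −15% |
| True start 30 min after charted, C0 before charted start | −4 to −10% | −9 to −24% |
| True start 15 min before charted | about 0% | −11 to −30% |
| Infusion runs 30 min longer than charted | −3 to −7% | −7 to −15% |
| True start after charted, C0 inside charted infusion | +5 to +11% | +2 to +86% |

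A second group of parameter sets, with C0 kept pre-dose, gave for 15 min shifts Vc −3 to −10% (one-compartment) and −12 to −26% (two-compartment). For 30 min shifts it gave −6 to −17% and −20 to −53%; the upper end is two-compartment with the dose charted late. If only the start is charted 30 min late, signs turn positive: CL +0.7 to +4.7%, Vc +1.9 to +19.3%.

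**Random charting error across subjects, RMSE (one- / two-compartment)**

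| Charting SD | CL | Vc |
|---|---|---|
| 0 | 4.6 / 5.0% | 10.8 / 18.1% |
| 15 min, C0 kept pre-dose | 5.7 / 5.5% | 13.0 / 26.3% |
| 30 min, C0 kept pre-dose | 7.2 / 9.2% | 20.1 / 48.8% |
| 15 min, raw times | 16.2 / 9.4% | 25.8 / 36.9% |

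**To AUC.** At linear steady state AUC24 = 200/CL, so the 50 and 100 limits correspond to CL 4 and 2 L/h. A CL error of −5% multiplies AUC by 1/0.95 = 1.053, which takes a true 95 to 100. CL −10% gives AUC +11%; CL +10% gives −9%.

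**The case against.** **The logged draws already bracket the infusion.** C0 precedes it, C1 marks its end, and both times are logged. Taking the infusion as running from C0 to C1, each drawn 5 min off, left CL error of 0 to +0.3% and Vc error of +0.1 to +1.2%. This is the strongest point and it stands for draws close to the infusion. But the plan states no such rule, and the rule leaves Vc error of −3 to −14% when C0 is drawn well before a delayed start.

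**The log may hold more than draw times.** A reader might infer that it holds only those. The text does not say so: the list in 5.10.2 opens with *including* and sits in a storage section. Staff could record dose times; they are simply not required to.

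**Administration records may be accurate.** A reader might infer that they carry only the ordered duration. No section says that. Section 5.8.5 names administration data as well as orders, and how the record captures starts, stops or pauses is not described. The size of charting error is therefore an assumption.

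**A one-way bias is not supported.** A reader might infer that charting ahead of the true start always makes CL too low and AUC too high. That holds only if C0 was drawn before the charted start. Section 5.7.1 puts C0 immediately before the dose; after a delayed start its logged time can fall inside the charted infusion, and the CL error becomes positive.

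**The effect on CL and AUC is modest.** This stands. At a random SD of 15 min with C0 kept pre-dose, CL RMSE barely moves. A systematic AUC shift near 10% would need most subjects mis-charted the same way by about 30 min, which no document suggests.

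**Conclusion.** The gap is real: draws are timed by observation, dose times come from abstraction, and no rule joins them. If charted times are off by 15 to 30 min, the main harm is to Vc. It is about 5 to 25% in most scenarios with C0 pre-dose, whichever way the charting errs; it reaches about 50% in two-compartment cases charted 30 min late, and can exceed that if C0 lands inside the charted infusion. Error in CL and AUC24 is smaller, about 0 to 10%, and its sign is not determined. These figures rest on assumed parameters, assumed charting error and a MAP approximation to the planned method. They show what is at stake and do not forecast bias in this study. The point is an inexpensive improvement that should be made, not a flaw that invalidates the analysis.

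**What to change.** This concerns data capture only; nothing about dosing or sampling times changes.

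- In 5.7.1, 5.10.2 and Appendix I 4.a.iv, have the study team member log the observed start, stop and any interruption of the sampled infusion, on the same clock as the draws.
- State in 6.1.1 that these logged times define the sampled dose in the Pmetrics data file, and that the administration record is used for earlier doses.
- Require any C0 timed after a charted start to be reconciled before modelling.

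The cost is a few extra fields on an existing log and a short reconciliation step. Section 7.3.2 already has a trained study team member take the samples, and C0 and C1 put that person near the start and end of the infusion. No added samples or visits are needed.
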